Relevance to proposed study. This study gave our team greater experience in recruiting inpatients following an ACS and successfully completing psychological and medical assessments by phone. Furthermore, it confirmed our hypotheses that positive psychological states and health behaviors are related. Finally, the results of this study helped to guide the development of our intervention (e.g., we shortened the intervention from a planned 12 weeks back to 8 weeks and included an exercise focused on past success).

PP for ACS: Proof-of-concept trial. This study was a one-arm, 8-week trial (IRB# 2013-P-001961) to test the feasibility of a PP intervention for patients recently admitted following ACS. The primary aim was to assess whether the intervention exercises were feasible and linked with immediate boosts in positive affect upon completion. The secondary goal was to assess whether the intervention impacted patients' psychological well-being at 8 weeks.

Methods. Participants completed questionnaires assessing positive psychological states, medical and functional status, and pre-admission health behaviors. Then they completed 8 weekly PP exercises, along with weekly phone calls with study staff to review the exercises. Finally, following the intervention, participants completed a follow-up assessment to assess for the same psychological, behavioral, and medical/functional states measured at baseline. We assessed the frequency of exercise completion and the pre/post exercise rating scales of positive states, as well as pre- and post-intervention psychological states, functional/medical states, and adherence to healthy diet, exercise, and medication behaviors.

Results. The intervention was feasible, as 74% of participants completed at least 5 out of 8 exercises, and the ease ($M = 7.4/10$; $SD = 2.1$) and utility ($M = 8.1/10$, $SD = 1.6$) of the intervention exercises were rated highly by participants.⁴¹ Additionally, compared to participants in a "treatment as usual" control condition, intervention participants showed greater improvements in positive affect, anxiety, and depression ($ds = .47-.71$).⁴¹

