For the PP portion of the intervention, the study trainer will (a) review the week's PP exercise (including the participant's ratings of pre- and post-exercise ease and helpfulness of the exercise), (b) discuss the rationale of the next week's PP exercise through a guided review of the PP manual, and (c) assign the next week's PP exercise. For the MI portion, participants will (a) review their physical activity goal from the prior week, (b) discuss techniques for improving physical activity, and (c) set a physical activity goal for the next week. The exercises and content for both PP and MI will be assigned in the same order for all participants receiving them.

Positive Psychology Exercises. The positive psychology exercises used in this study were selected based on their superior performance in our pre-pilot research and others' work, and have been organized into three sections by theme:

Gratitude-Based Activities:

Gratitude for Positive Events³⁰ (Session 1).

Participants recall three events, small or large, in the preceding week that were associated with satisfaction, happiness, pride, or other positive states.

Gratitude letter/Expressions of Gratitude³⁰(Session 2).

Participants write a letter of gratitude thanking a person for an act of kindness; participants may, at their discretion, share the letter with the other person.

Capitalizing on Positive Events^{71,72} (Session 3).

Participants recall three good events over the course of the week and then boost the positive feelings gained from them by sharing the events with others, or recording or celebrating the events in some way.

Using gratitude in daily life (Session 4).

Participants focus on implementing gratitude interventions and skills into daily life.

Strength-Based Activities:

Remembering past success/Remembering daily successes (Session 5).

Participants recall a prior event in which they experienced success. They then write about the event, the positive feelings evoked, the steps taken by the participant to contribute to the success, and the feelings generated by recalling the event.

Using personal strengths, part 1³⁰(Session 6).

Participants choose a personal strength and then use it in a new way over the subsequent week.

Using Personal Strengths, part 2³⁰ (Session 7).

Participants choose an additional personal strength and then use it in a new way over the subsequent week.

Using strengths in daily life (Session 8).

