- (b) Baseline physical activity (prior to hospitalization) will be measured with a modified version of the IPAQ to capture an estimate of the number of minutes spent performing MVPA in the past week (or a typical week, if the past 7 days atypical). The IPAQ has been used and validated in medical cohorts.^{58,59}
- (c) Medication adherence will be measured using the SRMA, a two-item measure of the percentage of time patients report taking their heart medications in the past one and two weeks.
- (d) Dietary adherence to a low-fat diet will be measured with the MEDFICTS scale recommended by National Cholesterol Education Program (NCEP). It is a widely-used and well-validated measure of cholesterol and saturated fat-intake.

Exercise ratings

We will obtain self-report ratings from participants for each completed exercise on two domains (ease of completion, overall utility). Participants will be asked to rate the ease (“how easy was the exercise to complete) and utility (“how helpful was the exercise”) of each exercise on Likert scales of 0-10 (0 = “not easy” or “not helpful,” 10 = “very easy” or “very helpful”).

VI. Biostatistical analyses:

A and B. Specific data variables and study endpoints

Aim 1: (*feasibility, acceptability*; primary aim): To determine whether the PP-MI intervention is feasible and acceptable by participants.

Measures:

- Rates of intervention completion (recorded by study trainer)
- Follow-up completion of self-report and objective adherence measures
- Measures of ease and utility

The intervention will be considered feasible if (1) at least 70% of all exercises are completed, (2) self-report follow-up data is obtained in 85% of participants, and (3) full accelerometer data is obtained in 80% of participants. The intervention will be considered acceptable if participants rate the PP exercises as at least 6/10 on ease and at least 7/10 on utility.

Aim #2 (between-group differences physical activity): To assess which group (intervention or control) is associated with the greatest physical activity at 12 (primary timepoint) and 24 weeks post-enrollment, as measured by self-report International Physical Activity Questionnaire (IPAQ).

Measures:

- Physical activity (IPAQ) (primary health behavior outcome measure)

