will also discuss any procedural difficulties, recruitment issues, and adverse events at this meeting (and before if needed). If there are consistent issues with the logistics, feasibility, or acceptability of recruitment, enrollment, follow-ups, or the intervention (e.g., participant complaints about length of follow-ups), we will review our methods and alter the study protocol as needed.

C. Outcomes monitoring

[name] (PI) will review study outcomes after four participants have completed the trial in order to assess the feasibility and acceptability of exercises and to ensure adequate completion of follow-up measures. If participants' completion or follow-up rates are far below the expected rates, if acceptability scores on the exercises are low, if optimism scores decrease following the exercises, or we sense more generally that some participants have been dissatisfied with the program, we will likely alter the protocol to address these issues. Further, we will preliminarily assess outcome measures after 20 participants have completed the study to ensure the feasibility and acceptability remains adequate and to monitor potential outcomes. We will then complete the more formal data analysis once all 48 participants have completed the trial.

D. Adverse event reporting guidelines

We will follow all PHRC guidelines with respect to reporting unanticipated problems, including adverse events. Specifically, when a serious or nonserious adverse event occurs, the PI will review the event to determine if it was possibly or definitely related to participation in the research. For all unanticipated problems and adverse events deemed related or possibly related to the research, we will complete and submit an Other Event report through Insight/eIRB as soon as possible and within 5 working days / 7 calendar days (as defined in the March 2014 Reporting Unanticipated Problems Including Adverse Events report). At Continuing Review, we will provide a summary of all unanticipated problems as per PHRC protocol. Finally, if there are unanticipated problems, especially if serious or recurrent, the PI ([name]) will amend the protocol if it is deemed necessary to protect the safety and welfare of the participants.

X. References

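### Does the loosely worded optimism trigger at the four-completer review need a definition and a before/after reporting rule?

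*Combined protocol and SAP*

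**What the plan says.** Section IX.C sets a review by the principal investigator once four participants have completed the trial. Its stated purpose is to check feasibility, acceptability and completion of follow-up. The reasons to amend the protocol are completion or follow-up rates well short of expectation, low acceptability ratings, and two more: "if optimism scores decrease following the exercises, or we sense more generally that some participants have been dissatisfied with the program, we will likely alter". A second look is planned: "we will preliminarily assess outcome measures after 20 participants have completed the study". It is meant to confirm feasibility and acceptability and to keep an eye on outcomes, and no action is attached to it. The section then says "We will then complete the more formal data analysis once all 48 participants have completed the trial".

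The closing paragraphs of Section IX.B open a second route to change. If the weekly team meetings find consistent problems with logistics, feasibility or acceptability, "we will review our methods and alter the study protocol as needed".

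The per-exercise data are described in two places. Section V.A (PP-MI condition) refers to "ratings of pre- and post-exercise ease and helpfulness of the exercise", and Section V.E (Exercise ratings) says "We will obtain self-report ratings from participants for each completed exercise on two domains (ease of completion, overall utility". The Aim 1 criterion in Section VI.A and B is numeric: "The intervention will be considered acceptable if participants rate the PP exercises as at least 6/10 on ease and at least 7/10 on utility". Optimism has no corresponding benchmark.

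**The concern.** Four people is a very small base for changing an intervention, and optimism is itself an Aim 3 outcome. Two optimism scales are collected (LOT-R and SOM), both arms do weekly exercises according to the control-condition text in Section V.A, and no size of fall is given. The phrase about scores falling after the exercises could even mean a rating taken around each exercise. The predecessor trial collected such ratings (Section I.B: "We assessed the frequency of exercise completion and the pre/post exercise rating scales of positive states"), but this protocol lists only ease and utility.

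Reporting is the larger worry. The pilot is meant to deliver Aim 1 feasibility rates and effect sizes for a larger multisite trial (Section VI.D). If the intervention were altered part-way, and all 48 participants were analysed together without comment, those figures would describe an undeclared mixture of versions. The model in Section VI.C has no term for protocol version.

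**Working it through.** The plan states no error rate or trigger probability for this review, so there is no figure of its own to reproduce. The check has four steps.

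**1. How undefined is the trigger?**
- Scale: the follow-up list in Section V.A and the Aim 3 list in Section VI both attach the plain label optimism to the LOT-R and call the SOM state optimism. The baseline list in Section V.A, which calls the LOT-R a measure of general optimism, leaves a little doubt.
- Timepoint: the exercises finish at about Week 12, which Section VI makes the primary timepoint for Aim 3.
- Arm: Section VIII.A describes exercises intended to raise optimism, and the Aim 1 acceptability criterion concerns the PP exercises. Both point to PP-MI.

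These are inferences, but sensible ones. What remains truly open is the size of fall.

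**2. How often would chance alone produce a fall?** Assume normal change scores and a true gain of d in SD-of-change units. The mean of n people falls with probability Φ(−d√n). At least one of four falls with probability 1 − Φ(d)⁴. The n = 2 column assumes 1:1 allocation, so that about half of the four are in PP-MI; the protocol does not state the ratio.

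| Assumed gain d | Mean of 4 falls | Mean of 2 falls | Any one of 4 falls |
|---|---|---|---|
| 0 | 50% | 50% | 94% |
| 0.2 | 35% | 39% | 89% |
| 0.5 | 16% | 24% | 77% |
| 0.8 | 5% | 13% | 61% |

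If a fall in the mean of either scale counted, the chance would be 63–70% at d = 0, and 23–27% at d = 0.5 with n = 4 (correlation between scales assumed to be 0.7 to 0.3).

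These figures lean high. The normal model allows no ties, yet Section V.E describes the LOT-R as a six-item scale of a fairly static trait, so unchanged scores are likely. The last column also needs an unlikely reading, in which one person's fall is enough.

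**3. Is optimism noisier than the other triggers?** Section I.B gives the predecessor's ratings as ease 7.4 (SD 2.1) and utility 8.1 (SD 1.6). If those SDs are between participants, which is an assumption, then with n = 4:
- mean ease below 6: Φ((6 − 7.4)/(2.1/√4)) = Φ(−1.33) = 9%
- mean utility below 7: Φ((7 − 8.1)/(1.6/√4)) = Φ(−1.38) = 8%

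With n = 2, each is about 17%. If the SDs are for single ratings, averaging over several exercises lowers these chances. Under the first reading they are of the same order as the 16% and 24% for optimism at d = 0.5. Removing optimism from the list would therefore not make a review of four people quiet.

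**4. What would splitting by version show?** Assume even accrual of 48 people over M months; the accrual time is not stated. When the fourth person finishes, 4 + (48/M) × t have started. With t = 5.52 months (Week 24), that is 26.1, 18.7 and 15.0 for M = 12, 18 and 24. With t = 2.76 months (Week 12), it is 15.0, 11.4 and 9.5.

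Take M = 18 and Week 24: 19 before and 29 after. The 95% half-width of a standardized group difference is 1.96 × √(4/n), with equal arms and no dropout:
- 19 before: 0.90 SD
- 29 after: 0.73 SD
- all 48: 0.57 SD

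The before-versus-after contrast has half-width √(0.90² + 0.73²) = 1.16 SD. In addition, (48/18) × 2.76 ≈ 7 of the 19 would be mid-intervention at the change and belong cleanly to neither version.

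**The case for a change.** The best case for acting is that the remedy is cheap. One sentence could require any change to be dated and results to be shown before and after it. The reviews could be confined to Aim 1 data, and the optimism clause dropped. On the text this case is right: no size of fall is stated, and nothing says how data from two versions would be combined. Review of amendments by the monitoring board (Section IX.B) is oversight, not a reporting rule. Should a change occur, neither version would be a trivial share of the 48.

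That much stands, but it does not carry the remedy. Dropping the optimism clause removes an early check for worsening in the very state the exercises aim to improve, and the monitoring board's listed reports do not cover optimism. Confining the 20-completer look to Aim 1 is a preference, because no action hangs on that look and no inflation of type I error is at issue. Step 4 shows that splitting Aims 2 and 3 by version would give estimates too imprecise to interpret. What is left is keeping a dated record of any change and showing Aim 1 rates by version. That is ordinary practice and needs no amendment.

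**Conclusion.** No change is called for. The wording is loose, but it describes judgement, not a decision rule. The sentence says only that alteration is likely, the companion triggers rest on terms such as low ratings or a general sense of dissatisfaction, and the review's stated purpose is feasibility. Adapting the intervention is legitimate in a pilot whose primary aim is feasibility and which says in Section VI.D that it is not powered for definitive group comparisons. Proposed amendments go to a monitoring board with psychiatry, cardiology and biostatistics members, which is a check on reacting to noise.

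The trigger chances of 16% to 77% at an assumed gain of 0.5 SD show how much depends on the reading. They are not the trial's probability of being altered, because they assume normal scores without ties and an automatic response to any drop. The missing reporting rule concerns a change that may never happen and that analysts would record and disclose if it did. A formal split of the efficacy estimates would gain nothing, given a before-versus-after half-width of about 1.16 SD on the assumed 19/29 division. This conclusion rests on the investigators disclosing any change when they report the pilot.

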It is exceedingly unlikely that a potential participant will be a patient currently in an investigator's clinical practice; however, if an investigator discovers that a potential participant is a member of his/her clinical practice, an alternate investigator will be substituted to provide a description of the study and obtain informed consent.

Finally, once patients sign the consent form, the investigator will perform a focused review of the patient's medical record (including laboratory data) to again confirm that the patient was admitted for ACS, and will consult with the study cardiologist in the event that there is any need for further clarification. If there is question about the patient's medical prognosis (to assess whether the patient has a condition likely to lead to death within 6 months) the study team will consult with the inpatient or outpatient treatment team and the study cardiologist.

Partners Healthcare has an electronic system that lets the participants' study doctors know if they are admitted to a Partners Hospital, or if they visit a Partners Hospital Emergency Department. We will use this system to ensure that the study doctors know about any possible problems or side effects participants experience while taking part in the study.

C. Treatment assignment/randomization

Participants will be randomized to receive the intervention or MI-based health behavior education (control) arm. They will be randomized by a random-number generator and will be assigned a condition after receiving baseline questionnaires when they return to MGH after discharge. The research assistant (RA)/blinded assessor who will conduct the follow ups will be blind to the study condition. The interventionist and subjects will not be blind to the study condition.

V. Study procedures

A. Study visits (See Table 1)

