Aim #3 (psychological, health behavior, and functional outcomes): To examine the impact of the PP-MI intervention on self-reported adherence measures, psychological outcomes, functioning, and health-related quality of life at 12 (primary timepoint) and 24 weeks post-enrollment.

Measures:

- Self-reported adherence (MOS-SAS)
- Cigarette Use
- Physical activity (IPAQ)
- Medication adherence (SRMA)
- Dietary adherence (MEDFICTS)
- Alcohol Use (AUDIT-C)
- Psychological outcomes:
 - Positive emotions (PANAS)
 - Optimism (LOT-R)
 - State Optimism (SOM)
 - Depression/Anxiety (HADS-D and HADS-A)
 - Stress (PSS-4)
- Medical outcomes:
 - Physical functioning (DASI)
 - Health-related quality of life (SF-12)
 - Cardiac Symptoms (WISE)

C. Statistical methods

Data will be downloaded from REDCap into the Stata statistical package.

For Aim #1 (*feasibility, acceptability*), descriptive statistics will be used to report the proportion of exercises completed and proportion of participants who provided follow-up information.

Descriptive statistics also will be used to determine mean ratings of ease and utility for each exercise. Significance will be set at $p < .05$, using two-tailed statistical tests.

For the Aim #2 analyses (between-group differences in MVPA), we will perform random effects regression analyses with a random intercept for each participant. We will include group, time, and group x time interaction variables and will control for baseline physical activity (as measured by IPAQ). This will allow us to include participants with some missing data.

For the Aim # 3 analyses (between-group differences on psychological, health behavior, functional, and quality-of-life outcomes), we will use a random effects regression model with a random intercept for each participant, as in Aim #2.

D. Power analysis

The study will likely not be powered to definitely test for between-group differences on the secondary outcome, but it should be adequate to generate effect sizes for a larger, multisite efficacy trial by the end of the grant period. We hypothesize that the intervention will have a moderate effect size on physical activity (vs. the control condition), based on similar effect sizes for psychological interventions in cardiac patients.⁹⁵⁻⁹⁷

VII. Risks and discomforts

A. Complications of surgical/non-surgical procedures

No surgical or non-surgical procedures are being used in this study.

B. Drug side effects and toxicities

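### Does the outcome review after 20 completers need a rule on whether results are pooled or shown by arm?

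*Combined protocol and SAP*

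**What the plan says.** Section IX.C (Outcomes monitoring) describes three steps.

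- **After four completers.** The PI "will review study outcomes after four participants have completed the trial in order to assess the feasibility and acceptability of exercises" and to confirm that follow-up measures are being completed. The triggers listed are low completion or follow-up rates, low acceptability scores, a fall in optimism after the exercises, and general dissatisfaction. If one occurs, "we will likely alter the protocol to address these issues".
- **After 20 completers.** The team will "preliminarily assess outcome measures after 20 participants have completed the study to ensure the feasibility and acceptability remains adequate and to monitor potential outcomes".
- **At the end.** "We will then complete the more formal data analysis once all 48 participants have completed the trial".

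Other sections bear on how the middle step is read.

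- VI.A and B, Aim 1 (the primary aim), defines feasibility as at least 70% of exercises completed, plus "self-report follow-up data is obtained in 85% of participants, and (3) full accelerometer data is obtained in 80% of participants". Acceptability rests on mean ease and utility ratings.
- VI.C gives the comparative model for Aim 2, on which Aim 3 is patterned: "We will include group, time, and group x time interaction variables and will control for baseline physical activity". It mentions no interim analysis.
- VI.D says the study is probably not powered for between-group differences, but "it should be adequate to generate effect sizes for a larger, multisite efficacy trial".
- IV.C says the "blinded assessor who will conduct the follow ups will be blind to the study condition". Interventionists and participants are not blind.
- IX.B, under the DSMB's monitoring of safety data, keeps unblinded data from investigators except where safety requires it.

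**The concern.** The 20-completer review has two purposes. Checking feasibility and acceptability can be done from completion rates and ratings. Monitoring potential outcomes appears to add something, yet the clause names no measure, no level of display and no action.

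A by-arm reading is possible. The only analysis specified for the Aim 2 and 3 outcomes is between-group, and calling the final analysis the more formal one could suggest that the look at 20 is a less formal version of it. On that reading, the team would see an arm difference with 28 of 48 participants (58%) still to finish, while it has power to amend the protocol. The trial's comparative product is a set of effect sizes for a later trial, so a reader of those estimates might ask whether anyone saw arm differences midway.

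**Working it through.** The plan states no interim alpha, power or detectable difference, so there is no figure to reproduce. The check sets the text side by side and then sizes what a by-arm look could show.

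**1. What the text supports.** The four-completer step is also described as a review of study outcomes, but its stated purpose is feasibility and acceptability. With four people it cannot be a meaningful arm comparison. So IX.C uses the word outcomes broadly. Its one trigger based on an outcome score, a fall in optimism after the exercises, is a within-person change and not an arm contrast. The 20-completer sentence is introduced as a continuation and asks whether feasibility and acceptability are still adequate. The natural reading is the same check on more people. This is an inference: the triggers are not restated for the second look.

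**2. Routes by which a by-arm look could do damage.**

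- *Early stopping or repeated testing.* No test or efficacy stopping rule is planned. For scale only: with information fraction 20/48 = 0.417 and correlation √0.417 = 0.645 between the two statistics, testing at two-sided 0.05 both times would give an overall type I error of about 0.086. With no interim test, none is added.
- *Outcome assessment.* IV.C blinds the follow-up assessor without exception, and nothing gives the assessor a part in the IX.C review.
- *Delivery.* Interventionists already know the arm. V.A fixes the order of PP-MI content for everyone who receives it, and calls in both arms are recorded, with a share reviewed for fidelity.
- *Protocol changes.* The grounds stated at the four-completer step are completion, follow-up, acceptability, optimism and satisfaction. Those at the end of IX.B are logistics, feasibility and acceptability. None is an arm difference.

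**3. What a by-arm look would show.** Assume 1:1 allocation (the plan states no ratio), so 10 per arm, and work in SD units.

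- Standard error: √(2/10) = 0.447.
- 95% half-width: 1.96 × 0.447 = 0.88 (normal), or 2.101 × 0.447 = 0.94 (t, 18 df).
- With an 8/12 split: √(1/8 + 1/12) = 0.456, giving 0.89 (normal) to 0.96 (t).
- At 24 per arm: 1.96 × √(2/24) = 0.57 (normal).

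VI.D calls the expected effect moderate without giving a number. Power of a two-sided 5% t-test at 10 per arm is:

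| Assumed d | Power |
|---|---|
| 0.3 | 10% |
| 0.5 | 19% |
| 0.6 | 25% |

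On the normal approximation, d = 0.5 gives 20% at 10 per arm and 41% at 24 per arm. An interval of about ±0.9 SD cannot separate a moderate benefit from no effect or a moderate harm.

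**4. What a pooled look would show.** The half-width for a mean of 20 is 1.96/√20 = 0.44 SD (normal) or 2.093/√20 = 0.47 SD (t). It says nothing about the arm difference.

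**The case for a change.** The best case for a change is that the clause is open, one sentence would close it, and the final report could then say that no comparative look was taken. The IX.B restriction on unblinded data does not settle the matter, because it sits under DSMB safety monitoring, IX.C does not refer to it, and in IX.C the study team itself does the reviewing. The four-completer step also shows that this team expects to change the protocol in response to what it sees.

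The factual part stands: no section says whether the look at 20 is pooled or by arm, and IX.B does not decide it. The consequence does not follow. Under every reading the descriptive primary aim and the single final analysis at 48 are unchanged, and the report can state what was looked at whether or not the protocol says so beforehand.

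Nor is the clarification as simple as it seems. Allowing outcome scores both pooled and within PP-MI would reveal the comparison it meant to exclude: with 10 per arm, the control mean is twice the pooled mean minus the PP-MI mean. Restating the assessor's blinding would add little to IV.C.

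**Conclusion.** The concern does not call for a change. IX.C leaves one detail unstated, and its context favours a non-comparative check of feasibility and acceptability. IX.B, although written for safety data, points the same way on investigators' access to unblinded results.

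If the team did look by arm, it would see a difference known only to about ±0.9 SD, with no rule attached to it. No planned estimate, test or conclusion changes. The figures assume 1:1 allocation and a range of d from 0.3 to 0.6 for an effect the plan does not quantify. They describe how little such a look could show and are not a measure of bias. The conclusion rests on the plan as written: no interim test, no efficacy stopping rule and one final comparative analysis. It would need revisiting if an interim arm comparison were used to stop the trial, alter it, or change its size.
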